- d A full physical examination will be performed at V1 and V24/ET. A brief physical examination will be performed at V17 and V27. Additional physical examinations will be performed only for assessment of signs or symptoms reported by the subject that might require further evaluation.
- e Height will only be measured at V1.
- f Serum pregnancy test for WOCBP will be obtained at V1. Subsequently, urine pregnancy tests will be performed at V5, V11/Last Titration, V14, V17, V20, V24/ET and V27. All positive urine results will be confirmed by a serum pregnancy test.
- g Chemistry blood samples and calculations:
- Complete Chemistry Panel will be obtained at V1, V5, V11/Last Titration, V14, V17, V20, V24/ET, V27. If a subject required adjustment of blood pressure medications during Screening, then a repeat Complete Chemistry Panel will be performed at V2.
 - Liver Chemistry Panel will be obtained at V1, V3-V24/ET, and V27. If a subject requires adjustment of blood pressure medications during Screening, then a repeat Liver Chemistry Panel will be performed at V2.
 - Serum creatinine will be obtained at V3, V4, V25 and V26.
 - eGFR will be calculated and reported whenever serum creatinine is obtained either as part of the Complete Chemistry Panel or when serum creatinine alone is measured.
 - Hepatitis B surface antigen (HBsAg) and hepatitis C virus antibody (Anti-HCV) will be obtained at V1 only.
- h Hematology blood samples will be obtained at V1, V5, V11/Last Titration, V17, V24/ET, and V27.
- i First morning, fasting urine specific gravity and osmolality (AM trough) will be obtained at V5, at every visit during the Lixivaptan Titration Period (except V11/Last Titration) and at V24 and V27. Dispense container and review instructions (including not to take study drug on the morning of the next visit) with subject at V4-V9, V23, and V26.
- j Trough (7-10 AM prior to AM dose) plasma specimens for measurement of lixivaptan will be obtained at V5, at the final visit during the Titration Period (V11/Last Titration), and during the Maintenance Period *if* ALT levels >3 x ULN and/or total bilirubin >2 x ULN occur.
- k Utilizing a separate informed consent, all subjects will be asked to provide a DNA sample at the end of the Baseline Period (V5) to assess genetic variants associated with hepatic abnormalities (if and when feasible).

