The expectation about the efficacy of lixivaptan in ADPKD is supported by the observed clinical effects of lixivaptan on the pharmacodynamic biomarker of urinary osmolality. Clinical studies conducted with lixivaptan in healthy subjects, ADPKD patients, and various other patient populations (patients with hypervolemic and euvoletic hyponatremia) demonstrated that treatment with lixivaptan readily suppresses urinary osmolality to levels below the target threshold of 300 mOsm/kg, irrespective of the specific patient population tested. Importantly, the magnitude of the effect observed with lixivaptan was comparable to the effect observed with tolvaptan in the same patient populations. In addition, like tolvaptan, treatment with lixivaptan was associated with a rapid-onset and fully reversible increase in serum creatinine. Taken together, these results suggest that treatment with lixivaptan can inhibit vasopressin receptor signaling to the extent necessary to observe clinical efficacy of a vasopressin antagonist for the treatment of ADPKD (Devuyst O 2017).¹⁴

Additional background information on the effect of lixivaptan on urine osmolality can be found in the IB.

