4.2.4 Reasons for Withdrawal

Reasons for withdrawal (subjects who refuse to return for any remaining study visits) or discontinuation (subjects who prematurely stop the treatment) at any time during the study may include, but are not limited, to the following:

1. No longer meet the protocol inclusion or exclusion criteria, e.g., require a prohibited concomitant medication.
2. Noncompliance with the protocol.
3. Lack of efficacy.
4. A serious or intolerable AE that, in the Investigator's opinion, requires withdrawal from the study, including but not limited to laboratory safety assessments that reveal clinically significant (CS) hematological or biochemical changes from the baseline values, other than changes that are expected for vasopressin antagonists, and symptoms of an intercurrent illness that justifies withdrawal. If the AE is related to abnormal liver chemistry test results, see [Section 7.3.7](#) for additional follow-up requirements. Mild elevations in serum creatinine or serum sodium are known pharmacodynamic effects of vasopressin antagonists like lixivaptan and are transient and reversible. Therefore, subjects should not be withdrawn from study participation solely due to mildly elevated serum creatinine or serum sodium. Cases where eGFR has declined by 25% or more from baseline should be discussed with the medical monitor and sponsor.
5. Death
6. Lost to follow-up.
7. Other (e.g., pregnancy, study burden, development of contraindication to use of study drug).
8. Withdrawal of consent (partial or complete).
9. Investigator's or Sponsor's decision to discontinue the subject's participation in the study.
10. Sponsor termination of the study.

Upon occurrence of an SAE or intolerable AE, the Investigator will confer with the medical monitor and Sponsor. If a subject is discontinued from study drug because of an AE, the

event will be followed until it is resolved or stable or up to 28 days as determined by the Investigator. Any subject may withdraw his or her consent at any time. Subjects' safety will be closely monitored throughout the study, and the study will be conducted following Good Clinical Practices (GCP). The entire study may be stopped at any time at the discretion of the Sponsor.

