6.3 Titration Period

The Titration Period will last from 3 to 6 weeks. Subjects will self-administer lixivaptan at home. All subjects will start at Level 1 (50 mg BID) and will be increased weekly over 2-5 weeks through Level 2 (100 mg BID), Level 3 (150 mg BID), and Level 4 (200 mg BID), as necessary, according to the schedule described in Table 4. If aquaretic effects limit a subject's tolerability at Level 3 (150 mg BID) or Level 4 (200 mg BID), dose levels can be adjusted to Level 3a and Level 4a, respectively, which reduce the evening (PM) dose by 50 mg (from 150 mg to 100 mg for Level 3 to 3a, and from 200 mg to 150 mg for Level 4 to 4a). Titration will stop when a tolerable dose level is reached that achieves the goal of lowering trough (first morning, fasting except for water) urine specific gravity to ≤ 1.005 or the highest dose (Level 4 or 4a) is achieved (regardless of trough urine osmolality). The minimum dose to enter the Lixivaptan Maintenance Treatment Period is Level 2. Once tolerability and reduced trough urine specific gravity are achieved (or tolerability and maximum dose), subjects will stay on that dose for 1 additional week under most circumstances to confirm tolerability (Table 5). Subjects will then proceed to Visit 11/Last Titration Visit.

6.3.1 Visits 6 to 10

Visits 6, 7, 8, 9, and 10 will occur weekly ± 3 days *as needed* for titration and may be conducted remotely by a HHC. Subjects will either report to the clinic or interact with a HHC in the morning for their visits (after a minimum 8-hour overnight fast except for water) to undergo Titration Period assessments. Note that telemedicine will be utilized at these visits for the Investigator to assess the subject's status and tolerability of the study drug and to make a titration decision. Any other issues may also be discussed with the subject.

[figure not shown]
Subjects should bring into the clinic, or provide to the HHC, any remaining study drug. Remind the subjects not to take their morning dose of lixivaptan on the morning of the visit in order to obtain a trough PK sample should they advance to Visit 11 procedures.

The following procedures will be performed at each visit unless otherwise noted:

- Collect and review concomitant medication information
- Review study drug compliance/reconciliation
- Assess study drug tolerability by asking the subject, "Are you able to continue this dose for the next 12 months?"
- Review lab results from prior visit

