7.3.7 Assessment of Liver Symptoms, Signs, or Test Abnormalities

Testing for hepatic transaminase (ALT/AST), alkaline phosphatase, and total and direct bilirubin will be performed at the timepoints as specified in the Schedule of Procedures (Table 1). Management of hepatic and liver chemistry test abnormalities are discussed below. *The appearance of any suspicious symptoms or signs of liver dysfunction as described in Appendix 4 (Section 13.4) in a subject at any time during the study should trigger prompt testing of liver chemistry tests (i.e., within 48 hours).*

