Shift table from baseline to worst post-baseline value according to abnormality assessed by investigators (normal, Clinically Significant (CS) and Not Clinically Significant (NCS)) will be presented for all applicable laboratory evaluations.

Potentially clinically significant results of clinical laboratory evaluations identified using prospectively defined criteria (Table 5) will also be summarized descriptively.

Lab Test Category	PCS Criteria		
	Sodium: <132 mmol/L		
	Sodium: >149 mmol/L		
	Potassium:<2.5 mmol/L		
	Potassium: >6.5 mmol/L		
	Calcium: <1.62 mmol/L		
Chemistry	Calcium:>3.49 mmol/L		
	Uric acid:>715 μmol/L		
	Albumin: <25 g/L		
	eGFR: Decrease from baseline of ≥25%		
	Glucose: ≤2.5 mmol/L		
	Glucose:≥14.0 mmol/L		
	Leukocytes: $\leq 2.5 \times 10^9/L$		
Hematology	Leukocytes: $\geq 15.0 \ge 10^9/L$		
	Neutrophils: $\leq 1.5 \ge 10^9/L$		
	Platelets: $\leq 50.0 \ge 10^9/L$		
	Hemoglobin: Decrease from baseline of ≥ 20 g/L		
	Hematocrit: Decrease from baseline of $\geq 10\%$ (absolute change)		
Urinalysis	Glucose: ≥2+		
	RBC/HPF: >10		
	Protein: >2+		
	Ketones: > 2 +		
	Leukocytes: >10		

Table 5: Potentiall	y Clinically	ly Important	Criteria ((PCS): Laboratory
	J		(

Abbreviations: RBC=Red Blood Cell; HPF=high power field.

Individual data listings of clinical laboratory results will be presented for each subject. Values outside of the clinical laboratory's reference range (i.e., those with low or high values) will be flagged in the clinical laboratory listings.

Abnormal laboratory results will be listed separately by all subjects.

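### Blood is drawn weekly during titration, but no serum sodium or creatinine is scheduled between Visit 5 and the last titration visit, so the plan's own eGFR and sodium criteria have no scheduled data during dose escalation

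*Protocol*

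**What the plan says.** **Schedule.** Protocol Table 1, footnote g, places the only panel that contains sodium as follows: "Complete Chemistry Panel will be obtained at V1, V5, V11/Last Titration, V14, V17, V20, V24/ET, V27". Creatinine on its own is scheduled outside the treatment period: "Serum creatinine will be obtained at V3, V4, V25 and V26". The weekly blood sample in titration is for a different panel: "Liver Chemistry Panel will be obtained at V1, V3-V24/ET, and V27". Section 7.3.7 describes what that panel covers: "Testing for hepatic transaminase (ALT/AST), alkaline phosphatase, and total and direct bilirubin will be performed at the timepoints". Table 6 likewise lists sodium and creatinine under the Complete Chemistry Panel and not under the liver panel. Section 6.3.1 names only the liver panel for the blood sample at Visits 6 to 10, and SAP Table 3 repeats the same schedule.

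**Expected effect.** Protocol Section 1.4 says that "treatment with lixivaptan was associated with a rapid-onset and fully reversible increase in serum creatinine". Sections 4.2.4 and 7.3.6 describe mild rises in creatinine and sodium as known effects of the drug class. Section 5.8 warns of dehydration and starts a fluid recommendation when titration begins.

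**Criteria.** Protocol Section 4.2.4 says: "Cases where eGFR has declined by 25% or more from baseline should be discussed with the medical monitor and sponsor". SAP Table 5 (Section 8.6.6) lists "eGFR: Decrease from baseline of ≥25" per cent among its potentially clinically significant criteria, along with sodium below 132 or above 149 mmol/L.

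**The concern.** The plan treats sodium and creatinine as analytes that the drug moves, and moves early for creatinine. It sets criteria on both sodium and eGFR. Yet it schedules neither measurement while the drug is started and escalated, although blood is taken at every one of those visits.

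Non-hepatic safety and tolerability is a secondary objective. A sodium or eGFR change that appears in titration and resolves, or is followed by a dose adjustment, before the last titration visit would leave no scheduled record. The protocol separates mild creatinine rises, which alone should not lead to withdrawal, from eGFR falls of 25% or more, which should be discussed. Telling one from the other needs a measurement. For scale, a subject whose baseline equalled the lowest permitted screening eGFR of 20 mL/min/1.73 m² would reach the discussion point at 0.75 × 20 = 15. The documents give no rate at which this would happen.

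**Working it through.** **Inputs.** Dosing paths from Protocol Table 5; visit spacing from Table 1 (weekly ±3 days in titration, every 28 ±3 days in maintenance); panel timing from footnote g; panel content from Table 6. Section 6.3.2 lets the Visit 11 procedures take place at an earlier visit once a subject qualifies for maintenance, so the end of titration is counted path by path. Visit 5 is week 0.

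**Reproducing the plan's figure.** Section 6.3 states: "The Titration Period will last from 3 to 6 weeks". The seven paths in Table 5 last 3, 4, 5, 5, 5, 6 and 6 weeks, which gives the same range.

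**Count for each path.** Interim visits with the liver panel only = weeks − 1. Dose ratio = peak daily dose ÷ 100 mg (the starting dose, 2 × 50 mg). The last column is the time from starting the peak dose to the first scheduled on-treatment sodium or creatinine, which falls at the last titration visit.

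| Path | Weeks from V5 to last titration visit | Interim liver-only visits | Peak daily dose (ratio) | Dose increases before first value | Weeks from start of peak dose to first value |
|---|---|---|---|---|---|
| 2 | 3 | 2 (V6–V7) | 200 mg (2) | 1 | 2 |
| 3 | 4 | 3 (V6–V8) | 300 mg (3) | 2 | 2 |
| 3a | 5 | 4 (V6–V9) | 300 mg (3) | 2 | 3 |
| 3a, second week of Level 3 not tolerated | 5 | 4 (V6–V9) | 300 mg (3) | 2 | 3 |
| 4 | 5 | 4 (V6–V9) | 400 mg (4) | 3 | 2 |
| 4a | 6 | 5 (V6–V10) | 400 mg (4) | 3 | 3 |
| 4a, second week of Level 4 not tolerated | 6 | 5 (V6–V10) | 400 mg (4) | 3 | 3 |

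- Every dose increase on every path comes before the first scheduled on-treatment value.
- Scheduled sodium or creatinine values strictly between Visit 5 and the last titration visit: 0.
- Scheduled on-treatment values in titration: 1 per subject, at its end.
- Next scheduled panel: Visit 14, the third maintenance visit, 3 × 4 = 12 weeks after the last titration visit.

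**With the two analytes added at Visits 6 to 10.** Scheduled on-treatment values in titration become 3 to 6 per subject, one for each week of the path. The longest scheduled gap in titration falls from 3–6 weeks to 1 week (±3 days).

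**The case against.** **The schedule is internally consistent.** Table 1, footnote g, Section 6.3.1 and SAP Table 3 agree, and a threshold can be applied to whatever values exist without implying weekly sampling. The panel is placed at the visit that confirms the final dose. This stands: no two schedule statements conflict. The gap lies between the schedule and the criteria.

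**Other checks exist.** Visits 6 to 10 include weight, blood pressure, heart rate, urine specific gravity and osmolality, adverse events, tolerability and a clinical check for liver dysfunction. A reader might infer that hydration and aquaretic effect go unmonitored in titration; they do not. None of these checks, however, yields serum sodium or eGFR.

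**Testing is possible.** A reader might infer that the criteria cannot operate at all in titration, or that discussion of a 25% fall is mandatory. Neither is supported. Protocol Section 7.3 permits extra safety tests at the investigator's discretion, a subject who stops early is due the Visit 24/ET panel, and Section 4.2.4 is worded as a recommendation. But the early-termination panel covers only those who stop, and SAP Section 8.1 keeps unscheduled results in listings and out of tables.

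**The rises are expected and reversible.** This explains why mild changes should not cause withdrawal. It does not explain leaving the interval unmeasured when larger eGFR falls are singled out.

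**Effect on the outputs.** A reader might infer that the planned tables of potentially clinically significant values would look too clean. SAP Section 9 reports early termination, with 6 participants in maintenance and no statistical analyses, and Appendix IV contains no such laboratory table; chemistry and eGFR by visit are listings only. That inference does not hold for the current SAP.

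**Conclusion.** A real gap in the schedule and a cheap improvement, not an error in the analysis. For 3 to 6 weeks of dosing, with the daily dose rising twofold to fourfold by path, the Section 4.2.4 eGFR discussion point and the SAP Table 5 sodium and eGFR criteria have no scheduled data. On the Level 4 and 4a paths the first scheduled value comes 2 to 3 weeks after 400 mg/day is started.

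The count assumes one visit per week and the paths in Protocol Table 5, which that section describes as the most common, not the only ones. It covers scheduled values only; how often investigators would have tested at their discretion is unknown. The documents do not show that any subject had an unseen abnormality, nor how frequent one would be. Early termination shrinks the practical effect on this study's report but does not alter the gap.

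**What to change.** Reconcile the assessment schedule with the plan's own criteria:

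- In Protocol Table 1, footnote g and Section 6.3.1, and in SAP Table 3, add serum sodium and serum creatinine (with calculated eGFR) to the sample already drawn for the liver panel at Visits 6 to 10.
- Report the results as scheduled values: in the chemistry and creatinine/eGFR listings under the reduced SAP Appendix IV, and in the SAP Section 8.6.6 tables if those are produced.
- Leave doses, thresholds and clinical responses as written.

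**Cost.** Two analytes on an existing sample and a schedule amendment, with no new visit or venepuncture. More values will be flagged, some of them expected pharmacology, which Sections 4.2.4 and 7.3.6 already address. Because the SAP reports that the study was stopped early, the change helps here only if titration visits remain. Protocol Section 1.8 says PA-ADPKD-301 uses the same dose range and titration scheme. Its assessment schedule is not in these documents and deserves the same check.

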1 INTRODUCTION

1.1 Background

Lixivaptan (also known as VPA-985, BIIB030, and CL 347,985) is a potent, non-peptide selective antagonist for the vasopressin V₂ receptor, which is expressed primarily in the collecting duct of the nephron (Chan PS 1998).¹ Lixivaptan antagonizes the effects of vasopressin that are mediated by the V₂ receptor, resulting in the pharmacologic effect of increased free water excretion, thus decreasing urine osmolality (U_{osm}), increasing urine flow, and increasing serum osmolality (S_{osm}) as well as restoring normal levels of intracellular cyclic adenosine 3',5'-monophosphate (cAMP) (Chebib FT 2015).²

The sponsor (Palladio Biosciences, Inc.) is currently developing lixivaptan for the treatment of autosomal dominant polycystic kidney disease (ADPKD). Lixivaptan had previously been under development for the treatment of symptomatic hypervolemic and euvolemic hyponatremia associated with heart failure and syndrome of inappropriate anti-diuretic hormone secretion.

Additional background information for lixivaptan can be found in the Investigator's Brochure (IB).

1.2 Overview of ADPKD

Definition

ADPKD is a hereditary kidney disorder characterized by cyst formation and progressive enlargement in the kidney, liver, and other organs. It results from loss-of-function mutations in either of 2 genes (*pkd1* and *pkd2*), encoding transmembrane polycystin 1 (PC1) and polycystin 2 (PC2), respectively.

In the kidney, loss-of-function mutations in *pkd1* or *pkd2* disrupt the normal differentiated phenotype of the renal tubular epithelium. These mutations lead to elevated intracellular levels of cAMP, which in turn results in increased cellular division and apoptosis, a loss of mitotic polarity, a disruption of the normal differentiated cellular phenotype, cyst formation, and fluid secretion into renal cysts (Antignac C 2015).³ The progressive development and growth of numerous bilateral renal cysts results in fibrosis, renal architectural derangement, and destruction of normal kidney tissue. Disease progression is characterized by urine concentration defects, hypertension, acute and chronic pain, kidney stones, haematuria, cyst and urinary tract infections, and, most importantly, renal function loss and kidney failure (Antignac C 2015, Chapman AB 2015).^{3,4}

The most frequent extrarenal manifestation of ADPKD is polycystic liver disease, which is typically associated with increased renal volume, older age, and female sex. Liver cysts are usually asymptomatic, and the liver chemistry is normal. However, in some cases the increased liver volume may lead to hepatomegaly as a result of the continuous cyst enlargement (Hogan MC 2015).⁵ This may cause symptoms of extrinsic compression, such as abdominal pain, early satiety, and obstruction of the hepatic veins or bile duct. Moreover, liver cyst infections cause fever, right upper abdominal pain, and possible elevated CA19.9 and alkaline phosphatase (ALP) levels.

Epithelial cells derived from human ADPKD cysts generate elevated intracellular levels of cAMP in response to vasopressin, which in turn promotes cell proliferation and electrolyte secretion (Belibi FA 2004).⁶ Increased fluid secretion into cysts is due to vasopressin-induced transepithelial secretion of chloride. Patients with ADPKD also have elevated plasma concentrations of vasopressin or an exaggerated vasopressin response to sodium challenge as compared to normal individuals (Torres VE 2005).⁷ Pharmacological interventions aimed at inhibiting vasopressin signalling are, therefore, expected to restore normal cellular function and provide a disease-modifying effect on disease progression in ADPKD.

1.3 Overview of Available Therapies for ADPKD

Demonstration of the utility of vasopressin V₂ receptor antagonists for the treatment of ADPKD is provided by the experience with tolvaptan. Results from the TEMPO 3:4 Phase 3 trial showed that tolvaptan slowed the progression of kidney enlargement and delayed the worsening of kidney function (Torres VE 2012).¹² The study also established suppression of urine osmolality to <250 mOsm/kg as a predictive pharmacodynamic marker of clinical efficacy for a vasopressin V₂ antagonist for the treatment of ADPKD (Devuyst O 2017).¹⁴ Subsequently, the REPRISE Phase 3 study with tolvaptan demonstrated that the efficacy of vasopressin V₂ receptor antagonism is maintained in patients with later stage ADPKD (Torres VE 2017b).¹⁵

The European Medicines Agency granted a positive opinion for tolvaptan (JINARC®) in 2015 to slow the progression of cyst development and failing kidney function in adult patients with ADPKD with normal to moderately-reduced kidney function who have rapidly progressing ADPKD. The Committee for Medicinal Products for Human Use recommended additional monitoring of the risk of liver damage with tolvaptan. Similar approvals were granted in Japan, Canada, and Australia/New Zealand.

In April 2018, tolvaptan (JYNARQUE®) was approved in the United States (US) to slow kidney function decline in adults at risk of rapidly progressing ADPKD. However, because of the risk of serious liver injury, Jynarque is only available through a restricted distribution program under a Risk Evaluation and Mitigation Strategy.

